### **3. INTRODUCTION**

#### **3.1. Preface**

This document presents a statistical analysis plan (SAP) for Betaliq, Inc. Protocol BTQ-1901-1902-201 (*A Randomized, Multicenter, Observer-Masked Study to Compare the Safety and Efficacy of BTQ-1901-A, BTQ-1901-B, and BTQ-1902 to Timolol 0.5% in Subjects with Primary Open Angle Glaucoma or Ocular Hypertension*).

Reference materials for this statistical plan include the protocol BTQ-1901-1902-201 (Version 1.0 Dated: 01JUN2020) and Case Report Forms (Final Version 4.0, dated 20JUL2021).

The SAP described hereafter is an *a priori* plan. The SAP will be finalized and approved prior to unmasking of any study data. Statistical programming may occur as study data accumulate in order to have analysis programs ready at the time the study finishes. In such an event, arbitrary treatment group assignments must be randomly linked to subjects, effectively rendering any output of programs meaningless.

For the reasons stated here the conduct of the study in the field is considered to be independent of any study outcome that might materialize upon enactment of the currently proposed statistical plan.

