## **5.3. Randomization and Masking**

A total of 240 eligible subjects will be randomized in a 1:1:1:1 ratio into 1 of 4 treatment arms and receive 1 drop in each eye BID, morning, and evening, for 84 days:

- BTQ-1901-A (nebivolol 0.5% ophthalmic suspension) (N = 60)
- BTQ-1901-B (nebivolol 1.0% ophthalmic suspension) (N = 60)
- BTQ-1902 (timolol 0.5% ophthalmic suspension) (N = 60)
- Timolol 0.5% ophthalmic solution (N = 60) [active comparator]

A randomized block design will be used, and the randomization will be created by a biostatistician independent of the trial. Randomization will not be stratified by any factors.

If subjects meet eligibility criteria at Visit 1/Screening as well as at Visit 3/Qualification/Baseline, sites will access the Interactive Web Response System (IWRS) to randomize subjects to study treatment and assign the study medication kit to be dispensed. The drug kit and randomization numbers will be recorded in the subject's eCRF. Study medication from the IWRS-assigned kit will be dispensed to the subject after initial dosing at the study site on Day 1 (Visit 3/Qualification/Baseline). The study will be observer masked.

Rules for unmasking a subject for safety reasons are fully described in the protocol and not repeated herein this SAP.

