### 9.1. Primary Efficacy Analysis

The primary efficacy analysis will be the between-group comparison of the mean IOP values in the study eye at each time point at each of the Visit 4/Day 15, Visit 5/Day 42, and Visit 6/Day 84 visits (i.e., a total of 9 between-group comparisons).

A summary of the efficacy endpoints will be prepared at each time point.

The between-treatment comparison will employ a mixed model for repeated measures (MMRM) with treatment, visit/time, treatment-by-visit/time interaction, and average baseline value as fixed effects, and actual IOP value in the study eye as the outcome variable of the model. Visit/time will include the following 9 timepoints: Visit 4/Day 15 (8:00 AM, 10:00 AM, 4:00 PM), Visit 5/Day 42 (8:00 AM, 10:00 AM, 4:00 PM), and Visit 6/Day 84 (8:00 AM, 10:00 AM, 4:00 PM). Average baseline value is the average result of IOP assessments performed at Visit 3/Day 1 (8:00 AM, 10:00 AM, and 4:00 PM).

An unstructured correlation matrix will be used thus allowing adjustment for correlations between time points within patients. A Kenward-Roger approximation will be used for the denominator degrees of freedom. If the model with the unstructured correlation matrix fails to converge then the following correlation structures will be fitted: variance components, compound symmetry, first order autoregressive and Toeplitz. The value of the Akaike Information Criteria (AIC) should be considered to choose the most appropriate model (the model with the smallest AIC is preferred). In case of inadequate results, further modification of the model may be required.

Example SAS code is provided below.

```
proc mixed data=eff method=reml;
  class trt visittime subjid;
  model actual=trt visittime trt*visittime avgbase/ddfm=kr;
  repeated visittime/type=UN subject=subjid;
  lsmeans trt*visittime/cl pdiff;
  run;
```

Where actual is the actual IOP value measured at each visit/time point, trt is treatment (BTQ-1901-A, BTQ-1901-B, BTQ-1902, or Timolol 0.5% ophthalmic solution), visittime is the combination of visit/timepoint (9 total values), and avgbase is the average baseline value.

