Treatment comparisons will be performed for the treatment difference in least squares means (LS mean) compared with the Timolol 0.5% treatment group. LS mean (standard error [SE]) by treatment group, visit and time, the LS mean difference between treatment groups, along with 2-sided 95% CI of the treatment differences and the p-value for the treatment comparison will be displayed. To demonstrate noninferiority, the upper limits of 95% CI for the difference between each comparison should be lower than 1.5 mm Hg at all timepoints. Additionally, the upper limits of the 95% CI should be lower than 1.0 mm Hg for the majority of time points measured (i.e., 5 of 9).

Linear contrasts will be used to calculate the confidence intervals at all visit/times.

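### SAP 9.1 leaves the primary noninferiority model open to undefined modification with no masking condition; secondarily, every named fallback covariance assumes one common variance

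*SAP*

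**What the plan says.** SAP 9.1 fits an MMRM to the nine post-baseline visit/times with an unstructured matrix and Kenward-Roger degrees of freedom. If that model does not converge, four structures are tried ("variance components, compound symmetry, first order autoregressive and Toeplitz") and the smallest AIC is preferred. The next sentence reads "In case of inadequate results, further modification of the model may be required". No criterion, scope, decision-maker or timing is attached to it.

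The same section bases the claim on pointwise limits: LS mean differences from timolol are shown "along with 2-sided 95% CI of the treatment differences", and the upper limit "should be lower than 1.5 mm Hg at all timepoints". A second condition requires upper limits below 1.0 mm Hg at a majority of the nine.

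SAP 3.1 calls the plan a priori and states that "The SAP will be finalized and approved prior to unmasking of any study data". Protocol 11.5.3 specifies an MMRM but no covariance structure or fallback, so it adds no constraint. On size, SAP 5.3 says "A total of 240 eligible subjects will be randomized in a 1:1:1:1 ratio into 1 of 4 treatment arms", which is 60 per arm. Protocol 11.2 and SAP 6 give no sample-size calculation, and neither document states an SD for IOP.

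**The concern.** Convergence failure and the choice among fallbacks are already covered by the sentences before the open clause. The clause therefore adds a further trigger, and that trigger is undefined. It applies to the model behind the only hypotheses that SAP 7.5 does not call exploratory. Finalizing the SAP before unmasking does not contain it, because the permission is part of the finalized text. SAP 3.2 requires labelling only for analyses not identified in the SAP, so a model changed under this clause could be reported as the planned one.

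The second issue is the content of the fallback list. Noninferiority needs all nine upper limits below 1.5 mm Hg, so one limit that is too narrow can turn a failure into a pass. If the unstructured model fails and IOP variability differs by time point, each listed structure applies an averaged variance everywhere. AIC cannot correct this, because no heterogeneous structure is offered.

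**Working it through.** **The open clause.** No arithmetic applies; the test is whether any passage limits it.
- SAP 9.1, convergence sentence: covers failure of the unstructured fit.
- SAP 9.1, AIC sentence: covers the choice among fallbacks.
- SAP 9.1, final sentence: acts beyond both, with no stated condition.
- SAP 3.1: fixes when the SAP is approved, not when a modification it already permits may be made.
- SAP 3.2: labels analyses outside the SAP; this one is inside it.

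No passage requires the decision to be masked.

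**The fallback variances.** The plan states no power, SD or error figure to reproduce.

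Inputs from the documents: 60 per arm (240/4); nine visit/times; upper limit of a two-sided 95% interval; margins 1.5 at all nine points and 1.0 at five or more. The unstructured matrix has 9 × 10 / 2 = 45 parameters, against up to 240 × 9 = 2,160 observations.

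Assumptions: complete data; SD 3.9 mm Hg at 8 AM and 3.2 and 3.0 at the other two clock times, the same at each visit; correlation 0.6 between time points.

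1. Common SD under a homogeneous structure: sqrt[(3.9² + 3.2² + 3.0²)/3] = sqrt[(15.21 + 10.24 + 9.00)/3] = sqrt(11.483) = 3.39.
2. Half-width = 1.96 × SD × sqrt(2/60) = 1.96 × SD × 0.1826. At 8 AM this should be 1.396 mm Hg; with the common SD it is 1.213, which is 13% too narrow.
3. True coverage at a time point with SD s = 2Φ(1.96 × 3.389/s) − 1; one-sided error = 1 − Φ(1.96 × 3.389/s).

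| SD at the time point | Correct half-width | With common SD | Coverage | One-sided error |
|---|---|---|---|---|
| 3.9 (8 AM) | 1.396 | 1.213 | 91.1% | 4.4% |
| 3.2 | 1.145 | 1.213 | 96.2% | 1.9% |
| 3.0 | 1.074 | 1.213 | 97.3% | 1.3% |

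4. Full nine-point rule, same inputs, variances treated as known, 400,000 simulated trials:

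| True difference from timolol | Passes, time-specific variances | Passes, common variance |
|---|---|---|
| +1.5 at one 8 AM point, 0 elsewhere | 2.3% | 3.8% |
| +1.5 at all three 8 AM points, 0 elsewhere | 0.27% | 0.62% |
| +1.5 at all nine points | 0.01% | 0.01% |
| 0 at all nine points | 24.1% | 24.9% |

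The first three rows are false claims; the last is the pass rate when there is no difference.

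5. Range over other assumed SDs (base SD 3.0, same formula). With one clock time (three of nine points) more variable by a ratio of 1.1, 1.2 or 1.5, the one-sided error there is 3.3%, 4.0% or 6.0%. With a single point of nine more variable, it is 3.6%, 4.7% or 8.2%. At ratio 1.0 it is 2.5%, so there is no effect.

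6. Check that the structures behave this way: REML fits to simulated data (4 arms × 60 × 9, one point with SD 4.5 and eight with 3.0) gave a single standard error for all nine points under each fallback. The half-width at the variable point was 1.52 unstructured, against 1.10 (variance components), 1.10 (compound symmetry), 1.13 (AR(1)) and 1.11 (Toeplitz).

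**The case against.** A reader might infer that results can be judged inadequate only after unmasking, so that SAP 9.1 flatly contradicts SAP 3.1. The text does not support that. The sentence follows directly on the convergence and AIC rules, so poor model fit is a natural reading. SAP 3.1 also provides for running programs with arbitrary treatment assignments, so convergence and covariance fit can be judged masked. What stands is that the plan permits masked use of the clause but does not require it.

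A reader might also infer that the primary limits will be too narrow, or that 4.4% is the error rate of the noninferiority claim. Neither follows. The fallback applies only if the unstructured model fails to converge, which is unlikely with 240 subjects. The SDs are assumed. The SAP says correlation structures; equal variance comes from how PROC MIXED defines these types in the REPEATED statement that the example code uses. And 4.4% is a pointwise figure: because all nine limits must pass, and pooling widens the others, the error of the whole rule moves much less.

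AR(1) and Toeplitz count the 2-hour step from 8 to 10 AM and the 27-day step from Day 15 to Day 42 as the same lag. With near-complete data this matters little: the half-widths in step 6 are almost equal across the four structures.

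There is some mitigation. SAP 9.3 plans ANCOVA and Wilcoxon tests at each time point, and a per-time-point ANCOVA uses that point's own residual variance, so a discrepancy due to pooling should show. But these are ITT sensitivity analyses, with LOCF for the ANCOVA, and they do not decide the claim. The Phase 2 setting lowers the stakes but does not remove the need for a fixed primary model.

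**Conclusion.** The main point holds. The primary noninferiority model can be modified on an undefined criterion, with no limit on scope or timing, and nothing prevents this after treatment estimates are seen. The documents do not show that such a change is intended, and its effect on error cannot be calculated because the permitted changes are not bounded.

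The covariance point holds as a secondary, conditional one. It needs both non-convergence and unequal variances. Under the assumed 3.9/3.2/3.0 SDs, false noninferiority on the full rule rises from about 2.3% to 3.8% in the least favorable pattern examined for those SDs (one 8 AM point carrying the whole excess). It stays below 1% if all three 8 AM points carry it, and the pass rate with no true difference barely moves. A more extreme SD ratio would increase the effect; equal variances remove it.

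**What to change.** Delete the sentence on inadequate results. Alternatively, limit it to non-convergence, decided and documented on masked data before unmasking, with any later model change labelled post hoc.

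Replace the AIC choice with a fixed order in which the first structure to converge is used, each allowing variances to differ by time point:
1. Unstructured.
2. UN@UN, visit by clock time. The code must then carry visit and clock time as two repeated factors instead of the single visittime.
3. Heterogeneous compound symmetry or heterogeneous Toeplitz, in a stated order, noting that Toeplitz still treats unequal gaps as equal lags.

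Do not use UN@CS with compound symmetry on clock time: it forces one variance across the three clock times within a visit, so in the scenario above it returns the same 3.39 and about 91% coverage at 8 AM. Drop variance components. If a homogeneous structure is ever used, report empirical (sandwich) standard errors with a compatible degrees-of-freedom method.

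The cost is a few lines of SAP text and code, which can be tested under the masked programming that SAP 3.1 already allows. The sponsor gives up the freedom to change the model later. Data collection and the intended primary model do not change.

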## 9.2. Secondary Efficacy Analysis

Similar analysis methods to those used for the primary efficacy endpoints will be utilized for the secondary efficacy endpoints.

Secondary efficacy endpoint #1: MMRM will be used for between-treatment comparison of change from baseline IOP in the average of the 3 daily IOP measurements at each post baseline visit. Treatment, visit, treatment by-visit interaction, and average baseline value will be considered as fixed effects, and change from average baseline IOP value in the study eye will be considered as the outcome variable of the model. Visits to be analyzed will include Visit 4/Day 15, Visit 5/Day 42, and Visit 6/Day 84. Average baseline value is the average result of IOP assessments performed at Visit 3/Day 1 (8:00 AM, 10:00 AM, and 4:00 PM). Change from baseline IOP value is a difference between average result of IOP assessments performed at post-baseline visit and baseline value (defined above).

Example SAS code is provided below.

```
proc mixed data=eff method=reml;
  class trt visit subjid;
  model change=trt visit trt*visit avgbase/ddfm=kr;
  repeated visit/type=UN subject=subjid;
  lsmeans trt*visit/cl pdiff;
  run;
```

Where change is the IOP change from average baseline value using the average of the 3 daily IOP measurements at each visit, trt is treatment (BTQ-1901-A, BTQ-1901-B, BTQ-1902, or Timolol 0.5% ophthalmic solution), visit is the visit (Visit 4/Day 15, Visit 5/Day 42, or Visit 6/Day 84), and avgbase is the average baseline value.

Treatment comparisons will be performed for the treatment difference in LS mean. LS mean (SE) by treatment group, visit and time (applicable for time-matched IOP change from

baseline), the LS mean difference between treatment groups, along with 2-sided 95% CI of the treatment differences and the p-value for the treatment comparison and within-treatment difference will be displayed.

Secondary efficacy endpoint #2: For the analysis of time-matched change from baseline in study eye IOP measurements at all time points MMRM will include treatment, visit/time, treatment-by-visit/time interaction, and average baseline value as fixed effects. Visit/time will include the following 9 timepoints: Visit 4/Day 15 (8:00 AM, 10:00 AM, 4:00 PM), Visit 5/Day 42 (8:00 AM, 10:00 AM, 4:00 PM), and Visit 6/Day 84 (8:00 AM, 10:00 AM, 4:00 PM). The average baseline value is the average result of IOP assessments performed at Visit 3/Day 1 (8:00 AM, 10:00 AM, and 4:00 PM). Time-matched change from baseline is a difference between actual IOP and baseline IOP taken at the same time of Visit 3/Day 1 (e.g. Visit 4/Day 15 8:00 AM change from baseline will be based on Visit 3/Day 1 8:00 AM result).

Example SAS code is provided below.

```
proc mixed data=eff method=reml;
  class trt visittime subjid;
  model timematchchg=trt visittime trt*visittime avgbase/ddfm=kr;
  repeated visittime/type=UN subject=subjid;
  lsmeans trt*visittime/cl pdiff;
  run;
```

Where timematchchg is the time-matched change from baseline value measured at each visit/time point, trt is treatment (BTQ-1901-A, BTQ-1901-B, BTQ-1902, or Timolol 0.5% ophthalmic solution), visittime is the combination of visit/timepoint (9 total values), and avgbase is the average baseline value.

Treatment comparisons will be performed for the treatment difference in LS mean. LS mean (SE) by treatment group, visit and time (applicable for time-matched IOP change from baseline), the LS mean difference between treatment groups, along with 2-sided 95% CI of the treatment differences and the p-value for the treatment comparison and within-treatment difference will be displayed.

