### 9.3. Sensitivity Analysis

Sensitivity analyses will be based on ITT population and will be performed for primary and secondary efficacy endpoints. This will include the same statistical methodology as in the primary and secondary analyses, however when using imputed data preliminary imputation steps will have to be completed prior to applying the methods from the primary and secondary analyses.

The following analyses will be performed:

- repeating the primary and secondary analyses;

- utilizing LOCF imputed data (see Section 7.3.2.3.1) and analysis of covariance (ANCOVA) model at each visit/time point;
- imputing missing data using multiple imputation techniques (see Section 7.3.2.3.2) and repeating the primary and secondary analyses;
- using Wilcoxon rank sum tests to compare treatments at each time point.

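### Secondary endpoint #2 subtracts the time-matched baseline but adjusts only for the three-time average, so its between-arm intervals can be wider than the data require (no bias, exploratory endpoint)

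*SAP*

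**What the plan says.** SAP 9.2 defines the endpoint #2 outcome thus: "Time-matched change from baseline is a difference between actual IOP and baseline IOP taken at the same time of Visit 3/Day 1". The model text says the "MMRM will include treatment, visit/time, treatment-by-visit/time interaction, and average baseline value as fixed effects", where the average is taken over the 8:00 AM, 10:00 AM and 4:00 PM readings at Visit 3. The example code agrees: "model timematchchg=trt visittime trt*visittime avgbase/ddfm=kr". Neither has a time-matched baseline term.

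Results come from "lsmeans trt*visittime/cl pdiff". LS mean differences and 95% CIs are shown at nine visit/times, and "the p-value for the treatment comparison and within-treatment difference will be displayed". SAP 9.3 lists "repeating the primary and secondary analyses" in the ITT population.

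Two neighbouring models differ in structure. For endpoint #1, "change from average baseline IOP value in the study eye will be considered as the outcome variable of the model", so the average subtracted is also the average adjusted for. The primary MMRM in SAP 9.1 has treatment, visit/time, their interaction "and average baseline value as fixed effects, and actual IOP value in the study eye as the outcome variable of the model", so nothing is subtracted.

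SAP 7.5 ties the noninferiority rule to the primary contrasts and labels all other comparisons exploratory. Protocol 11.5.3 says only that baseline values enter as fixed effects, and SAP 7.2.1 names baseline IOP as the covariate.

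**The concern.** Subtracting a baseline that is also a covariate does no harm, because the covariate's slope absorbs the subtraction. Here the subtracted quantity and the covariate differ. The part of the clock-time reading that the average does not explain is removed from follow-up IOP at full weight, whether or not it carries over to follow-up. If it is partly day-to-day or measurement variation, the subtraction adds noise to the outcome, and the model has no term to take it out again.

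What is at stake is precision at the nine endpoint #2 contrasts, in both the PP and ITT displays. A chance imbalance between arms in one clock-time baseline is likewise corrected at slope 1, not at an estimated slope.

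**Working it through.** The plan gives no figure to reproduce. SAP 6 says that the sample size rests on no formal calculation, and no SD or correlation appears. The inputs from the documents are the model (SAP 9.2), 60 subjects per arm (SAP 5.3) and the qualification window (Protocol 7.1: 22-34 mm Hg at 8:00 AM, 18-34 at 10:00 AM and 4:00 PM). All SDs and correlations below are assumed.

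**1. Structure.** Let Y be follow-up IOP, B the Visit 3 reading at the same clock time, A the three-time average, and D = B − A. The outcome is Y − B = Y − A − D. With A in the model, subtracting A changes nothing, so the SAP model is Y adjusted for A with the slope on D fixed at 1. The fuller model estimates that slope, b.

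**2. Formulas** (equal SDs, variance in units of follow-up variance). Let r be the correlation among baseline readings, m the baseline to follow-up correlation at the same clock time, and u that at other times.
- Var(D) = (2/3)(1 − r)
- b = (m − u)/(1 − r)
- Primary model, Y given A: P = 1 − (m + 2u)²/[3(1 + 2r)]
- Fuller model, Y given A and B: F = P − b² Var(D)
- SAP endpoint #2: S = F + (1 − b)² Var(D)

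The last term cannot be negative and is zero only at b = 1.

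**3. Worked example, r/m/u = 0.7/0.5/0.45.** Var(D) = 0.200 and b = 0.05/0.30 = 0.167. P = 1 − 1.96/7.2 = 0.728. F = 0.728 − 0.006 = 0.722. S = 0.722 + 0.694 × 0.200 = 0.861. The variance ratio is 0.861/0.722 = 1.19, and √1.19 = 1.09, so the CI is about 9% wider. With an assumed follow-up SD of 3 mm Hg, the half-width 1.96 × 3 × √(2V/60) is 1.00 mm Hg for S and 0.91 for F.

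**4. Other assumed scenarios, equal SDs.**

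| r/m/u | b | S/F | CI wider by | P/F (primary) |
|---|---|---|---|---|
| 0.6/0.55/0.55 | 0 | 1.45 | 21% | 1.000 |
| 0.7/0.5/0.45 | 0.167 | 1.19 | 9% | 1.008 |
| 0.8/0.5/0.45 | 0.25 | 1.10 | 5% | 1.011 |
| 0.8/0.6/0.45 | 0.75 | 1.01 | under 1% | 1.12 |
| 0.8/0.6/0.40 | 1 | 1.00 | 0 | 1.22 |

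Over r 0.6-0.8, m 0.5-0.6 and u 0.4-0.55 (never above m), the range is 0-21%.

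**5. Qualification window.** Simulated with an assumed pre-selection SD of 3.5 mm Hg and means of 24/22.5/22. For 0.7/0.5/0.45, the window lowers r to about 0.55 and m to about 0.38, and makes the baseline to follow-up SD ratio 0.75-0.86. CIs are 7.5-8.3% wider. For 0.6/0.55/0.55 they are 16-18% wider.

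**6. Bias.** Simulating the full model (4 × 60 subjects, nine visit/times, unstructured covariance, complete data, true difference 0, 300 replicates), the mean estimated difference was within 0.05 mm Hg of 0. It agreed between the two models to about 0.001. The model-based variance ratio for 0.7/0.5/0.45 was 1.19, as in step 3.

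**7. Why the added covariate must be centred.** LSMEANS sets a covariate to its mean over all records. With assumed baseline means of 25/23.5/23, that mean is 71.5/3 = 23.83. At b = 0.167 the slope of change on B is −0.833. A true change of −5 at 8:00 AM would then be displayed as −5 − 0.833 × (23.83 − 25) = −4.03. The simulation gave −4.04/−5.28/−5.71 across the three times uncentred, and −5.01/−5.01/−5.02 centred. Treatment differences are the same either way.

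**The case against.** The strongest reply is that nothing here is wrong. Text and code agree, the average baseline is the one covariate used throughout SAP 9.1 and 9.2, and adjusting a change score for it is valid. The precision is also often already on display. Under randomisation the primary contrast of actual IOP targets the same difference at the same nine visit/times. Where endpoint #2 loses most (first row of the table), the primary model is already as tight as the fuller one. After the fix, the between-arm contrast for change equals that for actual IOP under the same covariates. And where time-of-day deviations persist strongly, endpoint #2 as written is tighter than the primary.

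All of this stands. It limits the importance of the point but does not remove it: endpoint #2 still displays its own CIs and p-values, and they can be narrowed with data already collected.

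Stronger readings are tempting but unsupported.
- A reader might infer a biased treatment effect. The loss is in precision only, on average over randomisation.
- A reader might infer a threat to the noninferiority conclusion. SAP 7.5 does not use this endpoint for it.
- A reader might infer a conflict between documents. The protocol wording accommodates either covariate.
- A reader might infer that the intervals will usually be wider by a known amount. That would be a frequency over assumed correlations.
- A reader might infer that eligibility shrinks the loss simply by reducing the baseline SD. Holding correlations fixed, SD ratios of 0.85 and 0.7 give 0-15% and 0-11%. But selection lowers the correlations too, and the simulated window left 16-18% in one scenario, so those ranges are not the effect of eligibility.

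**Conclusion.** The point holds as a modest efficiency improvement, worth considering but not required. As specified, endpoint #2 fixes at 1 a slope that could be estimated. Asymptotically its between-arm interval is never narrower than under the fuller model. The excess cannot be determined from the documents and can be nil. The figures of 0-21%, 7-8% and 16-18% rest on the stated correlations, on equal SDs before any selection, and on the assumed pre-selection distribution. The closed form also takes the baseline readings as equally correlated. Any effect of per-protocol exclusions is a separate matter. The noninferiority decision and endpoint #1 are not affected.

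**What to change.** Before unmasking, derive `basetm_c`: the Visit 3 study-eye IOP at the record's clock time minus the mean Visit 3 IOP at that clock time over all analysed subjects. Change the endpoint #2 model line to

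`model timematchchg = trt visittime trt*visittime basetm_c basetm_c*visittime avgbase / ddfm=kr;`

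In the SAP 9.2 covariate sentence for endpoint #2, add the time-matched baseline centred within clock time and its interaction with visit/time, and keep the average. Carry the same model into the SAP 9.3 repeats of endpoint #2. This point asks for no change to endpoint #1 or to the primary MMRM.

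The cost is one derived variable, one model line and one sentence, with no new data. The model gains about 9 parameters with about 240 subjects. There are two drawbacks. The covariate set then differs from the primary model's. And only the LS means and within-treatment changes remain specific to this endpoint.
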